3.6. Validation of the Measurement Model and Data Analysis

The measurement validity of *wearables* will be checked against standard reference methods used at InCor, in order to verify the effectiveness of using *wearables* using parametric or non-parametric statistical tests, depending on the normality distribution pattern of the variables to be studied, considering p values <0.05 statistically significant.

The identification, sociodemographic and clinical data of the patients will be registered in the REDCap program, considered as a tool for managing and storing research data³¹ and analyzed using *Statistical Package for the Social Sciences* (SPSS) version 22.0 for Windows.

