The postoperative period of cardiac surgery requires continuous observation from the health team, quick decision-making and highly complex care. This period presents many challenges for the multidisciplinary team, due to the need for intensive/constant monitoring and the potential postoperative complications. In addition to the lives lost, these postoperative complications dramatically increase hospital and healthcare costs ⁸.

One of the most frequent complications in the postoperative period of cardiovascular surgery are arrhythmias, with atrial fibrillation being the most frequent arrhythmia in the postoperative period ⁹. The prevalence of postoperative atrial fibrillation (POAF) varies between 15 and 40% in coronary artery bypass grafting procedures, 37 to 60% in valve surgery and more than 60% in combined interventions and 24% in patients undergoing heart transplantation.

In 90% of cases, POAF appears in the first four postoperative days ¹⁰. The average length of the first episode is 7-8 hours. Recurrence occurs in 40% of cases and occurs within the first 24 hours. Up to 80% of patients remain in sinus rhythm

24 hours after the first episode. About 14% of patients with atrial fibrillation after cardiac surgery (AFACS) remain with this rhythmic disorder for up to two weeks ¹¹.

Other emerging evidence suggests that POAF is associated with long-term sequelae such as stroke, heart failure, and all-cause ¹²mortality.¹³

Despite the advances in the area and the different methods for monitoring POAF, there is still no method that allows the automated evaluation of fibrillation episodes for a very prolonged period. Thus, the detection of POAF becomes an important challenge.

Wearable devices such as *smartphones* and *smartwatches*, are a great promise for screening and monitoring AF, and can present up to 93% sensitivity and 84% specificity when compared to standard ECG ¹⁴. In addition, they are easy to use and allow evaluating the possible adherence of patients to this new modality of assisted telemonitoring. However, to be used as a medical device, these *wearables* need to be accurate in outpatient settings.

Technological resources for health solution

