In this way, not only the secure integration of the currently existing databases, but also the coherent use of the stored information, provide a valuable source of knowledge for a better understanding of patients treated by the SUS, thus allowing exploratory, prospective and retrospective studies to produce predictive models, and facilitating decision-making for better management of public health policies.

Wearable technology, such as the use of *smartwatches*, can capture valuable bioparameters, and that at the same time, EHR provides practical platforms for including these data - the creation of a graphical interface that displays patients' health data from these devices could both transform medical care and ensure patient privacy.

In view of the above, the present study aims, through the use of the **Smartwatch SAMSUNG™ Galaxy Watch5**, to validate a measurement model and data analysis that early indicate the need for medical assistance due to atrial fibrillation (AF) in individuals with heart disease undergoing cardiac surgery, as well as to evaluate patients' commitment to a new monitoring routine using regular

alerts based on automated readings, in comparison with the traditional postoperative routine.

The use of such devices as predictors of cardiac alterations could save the SUS hundreds of millions of reais per year, as it would avoid events in these individuals and, consequently, their treatment. To this end, this study will be randomized so that 50 patients will use a **Smartwatch device SAMSUNG™ Galaxy Watch5** and 50 patients will follow the institution's standard treatment (not monitored by wearables).

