2.2 Secondary objectives

- Evaluate the accuracy of the **Smartwatch SAMSUNG™ Galaxy Watch5** in detecting vital signs through optical sensors and, in particular, possible heart rhythm irregularities.
- Compare the results of the variables heart rate, blood pressure and peripheral oxygen saturation (SpO₂) and electrocardiogram provided by the **Smartwatch SAMSUNG™ Galaxy Watch5** with data obtained from gold standard reference equipment.

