3. METHODOLOGY

3.1 Place of study

This project will be carried out entirely on the premises of the Instituto do Coração of the Hospital das Clínicas of the Faculty of Medicine of the University of São Paulo. The sample will consist of 100 outpatients, with heart disease undergoing cardiac surgery, and selected during the pre -surgical consultation. The sample size was proposed by the contractor because it is a pilot study to evaluate the accuracy of the equipment in a sample with POAF.

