Phase 5	outpatient	
 Return outpatient consultation; Meeting with the project coordination team; Return of equipment used in the remote phase; ECG - smartwatch SAMSUNG ; SpO2 - smartwatch SAMSUNG + traditional oximetry; PA - smartwatch SAMSUNG + traditional auscultatory method; Quality of life questionnaire adapted to record the patient's perception during the remote monitoring phase; Issuance of a report confirming or not the classification of the ECG issued by the smartwatch;
phase 6	InCor	
 Description of tests carried out and compilation of final results; Definition, description and justification of the statistical tests chosen and aligned with the hypotheses raised at the beginning of the study.

Table 1: Protocol phases, locations and activities.

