3.8 Traditional electrocardiography (ECG) *versus* SAMSUNG smartwatch ECG

Still in phase 3 of the project, resting electrocardiography (ECG) tests will be performed in conjunction with ECG collection from the *smartwatch SAMSUNG*, for comparison between the two analysis methods (gold standard vs. device).

All electrocardiograms will be performed at a speed of 25mm/ sec, with 1mV/10mm calibration, in a MAC 2000 ECG Machine (GE Medical Systems Information Technologies, Inc., WI, USA) on an outpatient basis. The electrodes will be placed in the classic way of 12 leads (6 in the frontal plane D 1,D 2,D3,aVr,aVl,aVf and 6 in the horizontal plane V1,V2,V3.V4,V5,V6). The parameters will be evaluated by the clinical cardiologist, who will issue a report, based on the guidelines of the Brazilian Society of Cardiology on analysis and issuance of electrocardiographic reports.

3.9 Peripheral oxygen saturation (SpO₂) measurement by SAMSUNG *smartwatch* versus standard oximetry

SpO₂ values will be measured simultaneously by the *smartwatch* **SAMSUNG** and a digital pulse oximetry equipment (G-TECH 302L). Traditional oximetry, using an infrared light beam, simultaneously measures heart rate and peripheral oxygenation in percentages of 0-100%, and measurements above 95% will be considered normal. This evaluation will be carried out in phases 3 and 5 of the project.

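### Section 3.6 judges watch validity by unnamed significance tests at p<0.05; the plan gives no agreement statistic, sensitivity/specificity analysis or acceptance limit

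*Combined protocol and SAP*

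**What the plan says.** Section 3.6 is the only analysis text on watch validity in the material available for review. Validity is to be assessed "using parametric or non-parametric statistical tests, depending on the normality distribution pattern of the variables to be studied, considering p values <0.05 statistically significant", in SPSS 22.0. It names no test and does not say what a significant or non-significant result would mean for validity.

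What the analysis has to serve is stated elsewhere:

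- The Introduction gives as an aim "to validate a measurement model and data analysis that early indicate the need for medical assistance due to atrial fibrillation (AF") after cardiac surgery. As background, it reports that wearables "can present up to 93% sensitivity and 84% specificity when compared to standard ECG".
- Section 2.2 makes accuracy a secondary objective, comparing heart rate, BP, SpO2 and ECG from the watch "with data obtained from gold standard reference equipment".
- Section 3.1 says the sample size came from the contractor because "it is a pilot study to evaluate the accuracy of the equipment in a sample with POAF".
- The ECG section (the second one numbered 3.8) plans watch and 12-lead recordings in Phase 3 "for comparison between the two analysis methods (gold standard vs. device"). Section 3.9 plans simultaneous SpO2 readings, and section 3.10 plans repeated BP readings.
- Table 1 lists for Phase 5 "Issuance of a report confirming or not the classification of the ECG issued by the smartwatch", and for Phase 6 "Definition, description and justification of the statistical tests chosen and aligned with the hypotheses raised at the beginning of the study".

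**The concern.** A validation question asks how far the watch reading is from the reference, and whether that distance is tolerable. A p value from a test of zero mean difference, or of zero correlation, answers neither. For rhythm classification the natural measures are sensitivity and specificity, which the Introduction itself uses for other wearables, but section 3.6 plans neither.

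The comparison data are largely planned. Yet the study could end with paired readings and p values and no pre-specified basis for calling the watch accurate or inaccurate. Acceptance limits and BP pairing rules chosen after the data are seen lose most of their value as criteria.

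**Working it through.** **Plan's own figure.** There is nothing to reproduce. The 100 patients (50 with the watch, section 3.4) come with no effect size, SD, margin or precision target.

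**Text check.** Sections 3.5 to 3.11 contain numerical limits, but these are clinical normal ranges and alert thresholds, not limits on device error. The 93% and 84% are literature figures, neither a target nor a planned analysis.

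**Inputs for the illustrations.** n = 50 is from section 3.4 and two-sided 0.05 from section 3.6 (two-sided is my assumption). All biases, SDs and AF counts below are hypothetical.

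**1. Difference test, one pair per patient.** The noncentrality is bias × √50 / SD, with critical t(49) = 2.01. Limits of agreement are bias ± 1.96 SD.

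| Bias (mmHg) | SD of differences (mmHg) | Limits of agreement (mmHg) | P(p<0.05) |
|---|---|---|---|
| 2 | 3 | −3.9 to +7.9 | 99.6% |
| 2 | 5 | −7.8 to +11.8 | 79% |
| 2 | 8 | −13.7 to +17.7 | 41% |
| 2 | 15 | −27.4 to +31.4 | 15% |
| 5 | 15 | −24.4 to +34.4 | 64% |
| 8 | 15 | −21.4 to +37.4 | 96% |

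At equal bias, the noisier watch is flagged less often. The last two rows show that the test does pick up larger bias. What it misses is scatter.

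**2. Correlation test.** Critical r = t/√(48 + t²) with t(48) = 2.011, giving 0.279. With no bias and an SD of differences of 15 mmHg (limits ±29.4), expected r = s/√(s² + 15²), where s is the between-patient SD. That is 0.62 for s = 12 and 0.80 for s = 20, far above the threshold. In 20,000 simulated trials per setting, at least 99.9% were significant.

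**3. AF versus not AF.** The outcome is binary, so a choice by normality has no meaning. The number of patients in AF at the Phase 3 ECG cannot be derived from the documents. Applying 93% and 84% to whole patients gives these exact (Clopper-Pearson) 95% intervals:

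| In AF, of 50 | Sensitivity | Specificity |
|---|---|---|
| 4 | 4/4: 40–100% | 39/46: 71–94% |
| 10 | 9/10: 55.5–99.7% | 34/40: 70–94% |
| 20 | 19/20: 75.1–99.9% | 25/30: 65–94% |
| 30 | 28/30: 78–99% | 17/20: 62–97% |

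**4. BP pairing and repeats.** Section 3.10 lists 8 readings alternating between watch and cuff. It then lists three supine, one sitting and one standing cuff reading, without saying how the two sets relate. If the 8 readings formed 4 pairs per patient, and all 200 pairs were treated as independent, the error rate at zero bias would be 2Φ(−1.96/√(1 + 3ρ)). That is 12%, 22% and 29% for a within-patient correlation ρ of 0.2, 0.5 and 0.8. No passage plans such pooling; the figures show only why the handling of repeats must be stated.

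**5. Precision of the alternative.** With one pair per patient, the 95% interval for each limit of agreement is ± t(49) × √(1/50 + 1.96²/98) SD = 2.01 × 0.2433 SD, about ±0.49 SD.

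**The case against.** The wording does not commit the study to a difference or correlation test. An equivalence test would also fit it, so the figures above describe possible readings rather than a declared analysis. That is fair, but an equivalence test needs a margin and none is given.

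Several stronger readings are tempting, and the documents do not support them:

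- A reader might infer that watch and reference readings are unpaired throughout. Section 3.9 has SpO2 taken simultaneously, and the ECG section has the two recordings made together. The pairing gap is in BP only.
- A reader might infer that the Phase 3 ECG has no timing at all. Table 1 puts it in the surgical phase, listed with postoperative evaluation, discharge and device loan, so a time around discharge can be inferred. What remains is a conflict with the ECG section, which describes the recordings as outpatient.
- A reader might infer from the Phase 6 line in Table 1 that tests will be picked after the data are seen. It may mean only the write-up. Still, no available passage chooses them earlier.
- A reader might treat accuracy as the primary aim. Section 2.1 gives the telemonitoring platform as the primary purpose, and section 3.4 lists re-hospitalization ahead of the secondary outcomes. Accuracy is a secondary objective in a self-described pilot.

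The last point bears on severity, but does not remove the gap, because section 3.1 gives accuracy as the pilot's purpose.

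**Conclusion.** The point holds. Section 3.6 states a rule that, on its natural readings, cannot show whether the watch agrees with the reference, and no available passage supplies an agreement statistic, an accuracy analysis or an acceptance limit. With 50 pairs and a bias of 2 mmHg, the chance of p<0.05 falls from 99.6% to 15% as the SD of differences rises from 3 to 15 mmHg. The SDs, biases, AF counts and four pairs per patient are illustrations, not properties of the plan, and a few pages were removed before review. The defect should be corrected before analysis. Whether it ranks as essential or as strongly advisable is arguable: accuracy is a secondary objective, yet it is the stated reason for the pilot.

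**What to change.** Replace the sentence in section 3.6, before any data are seen, as follows.

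- **BP, heart rate and SpO2:** report mean bias and 95% limits of agreement with confidence intervals (Bland-Altman, by a method that allows for repeated readings within a patient). Judge them against acceptability limits the sponsor fixes in advance. Do not use p<0.05 as evidence of validity.
- **BP:** define which watch reading is paired with which cuff reading, and how the supine, sitting and standing readings enter. Report Phase 3 (just after calibration) and Phase 5 separately.
- **Heart rate:** name the reference, oximeter or ECG, and record the paired value. Section 3.9 says the oximeter measures heart rate, but does not make it the reference.
- **AF classification:** report sensitivity and specificity with exact 95% intervals from the paired Phase 3 ECGs. State that precision depends on how many patients are in AF then. Reconcile the Table 1 placement of that ECG with the outpatient wording in the ECG section.
- **Later phases:** report the Phase 5 confirmation of the watch ECG separately, since Table 1 lists no traditional ECG at that visit. State that Phase 3 pairs do not validate detection during remote monitoring.

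The cost is wording, recording of the heart-rate pair, and modest analysis of readings largely planned already, with no new patients or visits. The downside is that intervals may be wide: about ±0.49 SD for each limit with one pair per patient, and wide for sensitivity if few patients are in AF.

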3.7 Complete anamnesis

After confirming participation in the study, initial clinical examinations should be scheduled. Volunteers will be assessed for family and personal health history, and the variables to be collected are described in the case report Form (CRF) of the study (Annex 2).

3.8 Provision and use of SAMSUNG devices (smartphone *and smartwatch*)

SAMSUNG devices will need to be handed over to participants in phase 3 of the study in order for remote data collection to begin. Volunteers must sign a loan liability term that guarantees the return of the device, and coverage in case of damage, as per Annex 3. Longitudinal data collection will be carried out for a period of 30 days \pm 3 days, requiring remote monitoring by team. Smartphones and *smartwatches* will be used to monitor adverse events regarding cardiac arrhythmia, heart rate *and* blood pressure. All devices will be delivered with the necessary applications for data collection duly installed. However, customization (login and initial settings) will be carried out by the Innovation team. During phase 4, each participant will remain with **SAMSUNG** devices for 30 days \pm 3 consecutive days. Participants must use the *smartwatch* and *smartphone* throughout the day, including while sleeping, and charge the equipment batteries regularly. The data will be collected by an application embedded in the equipment.

During phase 5, the participant must return to InCor for a final consultation of the study, and return of borrowed equipment.

3.8 Traditional electrocardiography (ECG) *versus* SAMSUNG smartwatch ECG

Still in phase 3 of the project, resting electrocardiography (ECG) tests will be performed in conjunction with ECG collection from the *smartwatch SAMSUNG*, for comparison between the two analysis methods (gold standard vs. device).

All electrocardiograms will be performed at a speed of 25mm/ sec, with 1mV/10mm calibration, in a MAC 2000 ECG Machine (GE Medical Systems Information Technologies, Inc., WI, USA) on an outpatient basis. The electrodes will be placed in the classic way of 12 leads (6 in the frontal plane D 1,D 2,D3,aVr,aVl,aVf and 6 in the horizontal plane V1,V2,V3.V4,V5,V6). The parameters will be evaluated by the clinical cardiologist, who will issue a report, based on the guidelines of the Brazilian Society of Cardiology on analysis and issuance of electrocardiographic reports.

3.9 Peripheral oxygen saturation (SpO₂) measurement by SAMSUNG *smartwatch* versus standard oximetry

SpO₂ values will be measured simultaneously by the *smartwatch* **SAMSUNG** and a digital pulse oximetry equipment (G-TECH 302L). Traditional oximetry, using an infrared light beam, simultaneously measures heart rate and peripheral oxygenation in percentages of 0-100%, and measurements above 95% will be considered normal. This evaluation will be carried out in phases 3 and 5 of the project.

3.10 Blood pressure (BP) measurement by SAMSUNG *smartwatch* versus standard device

smartwatch will first be calibrated **SAMSUNG** for BP measurement following the instructions of the equipment itself. From then on, 8 consecutive measurements will be taken, at rest, alternating between using the *smartwatch* **SAMSUNG** and the arm pressure gauge (Brand *Welch*) standard, which uses aneroid meter and pulse auscultation (stethoscope *littman clinic*). Measurements with the standard device will be performed with the patient in the supine position, after 10 minutes of rest with 3 consecutive measurements. Additionally, a measurement will be performed in a sitting position and another measurement in an orthostatic position with a 30-second difference between measurements.

This assessment will be repeated in phase 5 of the project, following the same methodology described above.

3. 11 Definition of alerts – teleassisted group

The multidisciplinary team will receive alerts through the application platform, according to pre-established limits of blood pressure, heart rate and blood oxygen saturation.

- Blood pressure

Normal Parameters: Systolic [100 – 140 mmHg] and diastolic [70-90 mmHg]

Yellow Alert: Systolic [100 – 180 mmHg] and diastolic [90 – 110 mmHg]

Red Alert: Systolic [<90 and >180 mmHg] and diastolic [<60 mmHg and >100 mmHg].

- Heart Rate:

Normal parameters: HR detection between 60-100 bpm.

Red Alert: Detection of HR < 50 bpm outside sleep period; or HR > 100 bpm (concurrently assessed by watch)

- Oxygen Saturation:

Normal parameters: 95 – 100%

Yellow Alert: 91 – 95%

Red Alert: <90%

The conduct and actions planned to be taken by the clinical team after receiving the alerts through the Si3 platform (on D+1), as well as the guidelines that teleassisted patients will receive at the time of hospital discharge, are described in the table below:

INFORMAÇÕES AO PACIENTE

INFORMAÇÕES À EQUIPE CLÍNICA

[figure not shown]
	SITUAÇÃO	ORIENTAÇÃO	INTERVENÇÃO	AÇÃO
	Detecção de FC < 50 bpm fora do período de sono	Realizar medidas de parâmetros indiretos (ECG, P.A. E SPO ²)	Entrar em contato com a enfermeira da equipe pelo telefone	Analisar os parâmetros clínicos e os sintomas do paciente. Enfermeira aciona teleconsulta com o médico se necessário. Em caso de necessidade, o médico orienta o paciente a procurar o PS do InCor
	Detecção de FC > 100	Realizar medidas de parâmetros indiretos (ECG, P.A. E SPO ²)	Entrar em contato com a enfermeira informando o ocorrido	Orienta o paciente a procurar o PS do InCor
	PAS: Sistólica < 90 e > 180 mmHg	Realizar medidas de parâmetros indiretos (ECG, P.A. E SPO ²)	-	Orienta o paciente a procurar o PS do InCor
	PAS: Diastólica < 60 e > 110 mmHg	Realizar medidas de parâmetros indiretos (ECG, P.A. E SPO ²)	-	Orienta o paciente a procurar o PS do InCor
	PAS: Sistólica 140 - 180 mmHg	Realizar medidas de parâmetros indiretos (ECG, P.A. E SPO ²)	Entrar em contato com a enfermeira da equipe pelo telefone	Analisar os parâmetros clínicos e os sintomas do paciente. Enfermeira aciona teleconsulta com o médico se necessário. Em caso de necessidade, o médico orienta o paciente a procurar o PS do InCor
	PAS: Diastólica 90 - 110 mmHg	Realizar medidas de parâmetros indiretos (ECG, P.A. E SPO ²)	Entrar em contato com a enfermeira da equipe pelo telefone	Analisar os parâmetros clínicos e os sintomas do paciente. Enfermeira aciona teleconsulta com o médico se necessário. Em caso de necessidade, o médico orienta o paciente a procurar o PS do InCor
	SPO ² : 91 - 95%	Realizar medidas de parâmetros indiretos (ECG, P.A. E SPO ²)	Entrar em contato com a enfermeira da equipe pelo telefone	Analisar os parâmetros clínicos e os sintomas do paciente. Enfermeira aciona teleconsulta com o médico se necessário. Em caso de necessidade, o médico orienta o paciente a procurar o PS do InCor
	SPO ² : <90%	Realizar medidas de parâmetros indiretos (ECG, P.A. E SPO ²)	Entrar em contato com a enfermeira da equipe pelo telefone	Orienta o paciente a procurar o PS do InCor
	Sono: < 7 horas contínuas	N/A	Entrar em contato com a enfermeira da equipe pelo telefone	Analisa a possível causa e fornece orientação de Higiene do Sono
	Passos: <500 passos	N/A	Entrar em contato com a enfermeira da equipe pelo telefone	Analisa a possível causa e orienta o paciente a aumentar o nº de passos

Table 2. Flow of care for patients in the study (alerts, guidelines, interventions and actions)

The institutional electronic medical record (Si3) software modeling that will be used in the project to access clinical and functional information regarding patient data, are exemplified in the figures below:

Figure 6. Institutional Electronic Health Record: Macro view of the alerts referring to the teleassisted group .

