3.4 Selection of volunteers

Patients with heart disease undergoing cardiac surgery, monitored at the InCor outpatient clinic. Randomization will be performed 1:1 using an electronic randomization system and subsequently stratified from the RedCap platform, without knowledge by the team involved in the study. Patients will be randomized to intervention group (teleassisted group) or control group (standard follow-up of the institution)

1. **Control group (N=50):** patients with heart disease who underwent a surgical procedure with standard outpatient and post-surgical follow-up, according to institutional routines and protocols;
2. **Tele-assisted group (N=50):** patients with heart disease undergoing a surgical procedure remotely monitored through *smartwatch* and application.

Adult patients will be included, of both sexes, and ethnic profile representative of the Brazilian population, characteristic of the user population of the Unified Health System (SUS).

re-hospitalization rate, through scheduled consultations and extra interurrences (clock x institutional standard). As secondary outcomes will be evaluated: technological and treatment adherence, through the use of the mobile application by patients and development and implementation of the telemonitoring platform.

The goal is the inclusion of 40 patients/month (in all, in the 2 study groups: Remotely monitored watch group and group without a watch, following the institutional standard, following the randomization order generated by a specific

system) with 20 in each group of the study. In addition, the inclusion of patients will happen gradually and continuously, with 1 patient per group/working day.

Sem 1	Sem 2	Sem 3	Sem 4	Sem 5	Sem 6	Sem 7	Sem 8	Sem 9
1 ao 5	6 ao 10	11 ao 15	16 ao 20	21 ao 25	26 ao 30	31 ao 35	36 ao 40	41 ao 45
						1 ao 3	4 ao 8	9 ao 13
Sem 10	Sem 11	Sem 12	Sem 13	Sem 14	Sem 15	Sem 16	Sem 17	
46 ao 50								
14 ao 18	19 ao 23	24 ao 28	29 ao 33	34 ao 38	39 ao 43	44 ao 48	49 ao 50	
● Inclusão ● Retorno								

Figure 3. Flow of inclusion of patients in each arm of the study.

The remote patient monitoring flowchart to be used in this project is shown in Figure 3. Briefly, it includes:

1. Preoperative outpatient consultation with complete anamnesis to verify eligibility for using the **SAMSUNG™ Galaxy Watch5 Smartwatch**;
2. Hospitalization, surgery and collection of intraoperative data;

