3.5 Data collection, clinical examinations and evaluation of results

In this project, wearable devices such as the Galaxy Watch will be used. 5 together with Galaxy series smartphones (A or S line) for the acquisition of blood pressure measurements, arterial hemoglobin oxygen saturation (SpO2), heart rate and ECG. This data will be transmitted to a repository, in a secure cloud environment, which meets the requirements of the General Data Protection Act

(LGPD) (Figure 5). In addition, data will be transmitted to a platform to be developed by InCor's IT team, as part of the project, and integrated into InCor's electronic medical record through the WebAdmin tool .

[figure not shown]

Figure 5 . Conceptual diagram for the Telemonitoring Platform.

The division of the study into phases and activities was carried out according to the table and description below.

Phase	Local	Activity
Phase 1	outpatient	
 • Inclusion of patients • Preoperative consultation; • Meeting with the project coordination team; • Complete anamnesis; • Application of the TCLE; • Collection of additional and contact information;
Level 2	hospitalization	
 • Hospitalization; • Eventually, some patients may be included in the study after hospitalization, prior to surgery, with the application of informed consent at this time;
phase 3	surgical	
 • Performing the surgical procedure; • Intraoperative data collection; • Postoperative evaluation and discharge • Patient guidelines; • Signature of the equipment loan liability term (smartphone and smartwatch); and the term for using data from the Electronic Health Record; • Calibration: 
 - BP, serial measurements - smartwatch SAMSUNG + traditional auscultatory method; - ECG - smartwatch SAMSUNG + traditional ECG; - SpO2 - SAMSUNG smartwatch oximetry + traditional oximetry; • Questionnaire of events observed during the remote phase;

Phase 4	remote collection	
 Tracking, monitoring and managing each participant's remote data collection for 30 ± 3 days; these being: 
 - Automatically collected: SpO2, heart rate, steps and sleep. - Collected manually: blood pressure and ECG. Telephone contact, teleconsultations, and unscheduled face-to-face consultations in cases of complications;

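### The watch is checked against reference devices only at supervised visits, no analysis is planned at the alert limits, and the red SpO2 and systolic limits would be almost untested

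*Combined protocol and SAP*

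**What the plan says.** The Introduction says that wearables used as medical devices "need to be accurate in outpatient settings". Section 3.1 gives the basis for the sample: "The sample size was proposed by the contractor because it is a pilot study to evaluate the accuracy of the equipment". Only the tele-assisted arm of 50 patients is monitored with the watch.

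The reference comparisons are:

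- **Blood pressure (3.10).** After calibration, "8 consecutive measurements will be taken, at rest, alternating between using the" watch and the arm device. The standard readings are made "with the patient in the supine position, after 10 minutes of rest with 3 consecutive measurements", followed by one sitting and one standing reading. Whether the watch is read in those two postures is not clear. The procedure is repeated in phase 5.
- **SpO2 (3.9).** Watch and oximeter are read simultaneously: "This evaluation will be carried out in phases 3 and 5 of the project". The oximeter also gives heart rate.
- **ECG (3.8 and Table 1).** A resting 12-lead ECG is paired with the watch ECG in phase 3. For phase 5, Table 1 lists the watch ECG and a report on its classification, but no reference recording.

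For remote phase 4, Table 1 lists calls, remote consultations and "unscheduled face-to-face consultations in cases of complications". No paired reading is mentioned. Section 3.11 sets alert limits for blood pressure, heart rate and SpO2, but none for ECG or atrial fibrillation. Table 2 directs patients to the emergency department for the red systolic, diastolic and SpO2 readings and for heart rate above 100.

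Section 3.6 says only that parametric or non-parametric tests will be used, "considering p values <0.05 statistically significant". It plans no agreement or accuracy analysis by alert band.

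**The concern.** The alerts act on unsupervised home readings, and the red ones act on extreme values. The device is validated at two supervised visits, around discharge and about 30 days later. The patients seen there have had a narrowing exclusion applied: section 3.3 removes those with complications and a stay of more than 14 days. Error near normal values is weak evidence about error far from normal, and it gives no evidence on performance during home use.

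If results are pooled over all pairs, near-normal readings will dominate. A good overall figure would then invite the conclusion that the red alerts work, when few or no pairs lay beyond those limits. Because red readings lead to emergency referral, this is the accuracy claim a later user would most want to rely on.

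**Working it through.** **What can be reproduced.** The sample size has no stated precision or power, so only 50 + 50 = 100 can be checked. What can be calculated is how many pairs would fall in each band.

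**Inputs.** From the documents: 50 watch patients, two visits and the alert limits. This gives at most 50 × 2 = 100 patient-visits, counting one pair per visit and no dropout. Repeat readings at one visit add pairs but no new patients. The means and SDs below are assumptions, because the documents give none.

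**Formula.** Expected pairs per 100 = 100 × Φ((limit − mean)/SD) for a lower limit, 100 × [1 − Φ((limit − mean)/SD)] for an upper limit, and the difference of two such areas for a band.

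| Band | Assumed mean/SD | Expected per 100 pairs |
|---|---|---|
| SpO2 <90% (red) | 97/1.5 (z = −4.67); 96/2 (z = −3.00); 95/2 (z = −2.50) | 0.0; 0.13; 0.62 |
| SpO2 91–95% (yellow) | same three | 9; 30; 48 |
| Systolic <90 (red) | 120/15 (z = −2.00); 125/18 (z = −1.94); 115/15 (z = −1.67) | 2.3; 2.6; 4.8 |
| Systolic >180 (red) | same three (z = 4.00; 3.06; 4.33) | 0.00; 0.11; 0.00 |
| Systolic 140–180 (band acted on in Table 2) | same three | 9; 20; 5 |
| Diastolic <60 (red) | 80/10 (z = −2.00) to 68/10 (z = −0.80) | 2.3 to 21.2 |
| Heart rate >100 (red) | 75/12 (z = 2.08) to 90/12 (z = 0.83) | 1.9 to 20.2 |

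**Sensitivity.** With SpO2 mean 94, SD 2, and values below 89.5 counted as below 90%, the tail is 0.0122, or 1.2 per 100. With systolic mean 130, SD 18, the figures are 1.3 per 100 below 90 and 0.3 per 100 above 180. The picture does not change.

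**Without a distribution.** If a proportion p of the 50 patients lies in a red zone at a visit, the expected number is 50p and the chance of none is (1 − p)^50:

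- p = 1%: 0.5 expected, 60% chance of none
- p = 2%: 1 expected, 36% chance of none
- p = 5%: 2.5 expected, 8% chance of none
- p = 10%: 5 expected, 0.5% chance of none

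**What small numbers can show.** If all n true cases are detected, the exact lower 95% limit for sensitivity is 0.025^(1/n). This is 2.5% for n = 1, 16% for n = 2, 48% for n = 5 and 69% for n = 10.

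**Bands that cannot yet be tabulated.** The list in 3.11 gives yellow systolic as 100–180, which overlaps normal (100–140), while Table 2 uses 140–180. The upper red diastolic limit is above 100 in the list and above 110 in Table 2. With diastolic mean 80, SD 10, that difference alone moves the expected count from 2.3 to 0.1 per 100. The number of blood pressure pairs is also unclear: eight alternating readings give four per device, but the standard readings described are 3 + 1 + 1 = 5.

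**The case against.** A reader might infer that values at the alert limits in general will hardly occur, so that the whole alert system goes untested. The documents do not support that. They give no distribution of vital signs, and under the assumptions above the yellow SpO2 and systolic bands hold 9 to 48 and 5 to 20 of 100 pairs. Diastolic below 60 and heart rate above 100 may also be reasonably represented. A reader might also extend the point to ECG alerts, but section 3.11 sets no ECG limit. For ECG the point is only that no reference recording is listed after phase 3. Nor is it right to say that blood pressure is taken only supine, since a sitting and a standing reading are planned.

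The other side also has these arguments:

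- This is a declared pilot, and the accuracy objectives in 2.2 concern agreement with reference equipment, not alert thresholds. That excuses small numbers in a band. It does not excuse leaving the limit of the claim unstated, since 3.1 gives accuracy as the reason for the study.
- The Introduction's outpatient settings need not mean unsupervised home use, and phase 5 is itself an outpatient visit. This is fair, so the point rests on where alerts are raised, not on that phrase.
- Pairs taken at alert-triggered attendances are a selected sample. They may come after the value has returned to normal, because 3.11 has the team acting on the next day, and they cannot reveal missed events. This stands, so such pairs can only be supplementary.

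**Conclusion.** The point holds in limited form and should be addressed. It is certain from the text that no described comparison takes place under remote use or when an alert fires, and that no analysis by alert band is planned. Scarcity of pairs is supported for SpO2 below 90% (about 0 to 0.6 of 100) and systolic above 180 (0 to 0.1), and roughly for systolic below 90 (2 to 5).

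These counts assume normal distributions with the stated means and SDs, one pair per patient-visit, full attendance and watch readings in the tele-assisted arm only. Real tails may be heavier than normal. If control patients were also measured with a watch, the counts would double and the red SpO2 and upper systolic bands would still be nearly empty. The consequence is a risk of over-reading the accuracy result. It does not show that the watch is inaccurate.

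**What to change.** 1. Reconcile the blood pressure bands between the list in 3.11 and Table 2. Also reconcile the number and posture of paired readings in 3.10, saying whether the watch is read sitting and standing.
2. In 3.6, plan agreement between watch and reference for blood pressure, SpO2 and heart rate (using the oximeter's heart rate) by alert band, with the number of pairs and of patients in each. Say which reading defines the band.
3. Set in advance the minimum number of patients for a band to be evaluated. State that accuracy is not evaluated in bands below it, and limit the main accuracy claim to supervised spot readings.
4. Where feasible, record the watch reading beside the standard reading taken at unscheduled attendances at the institute. Report these separately as supplementary agreement data, not as sensitivity.

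Items 1 to 3 need no extra patients or visits and cost some drafting and one table. The headline claim becomes narrower. Item 4 is optional and needs a few minutes of staff time outside the planned visits.
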